ii. Mode Comparisons: Using the optimal frequency(ies) identified, we will compare the effects of continuous versus the 4 Hz pulsed modes for 10.7 minutes each in counter-balanced order across patients measuring the rate of swallowing and ratings of the urge to swallow to identify the most effective mode of stimulation.

iii. Pressure Comparisons: Using the Iowa Oral Performance Instrument to measure strap to neck pressure and calipers to measure neck tissue fat, the effects of 2, 4, and 6kPa on rate of swallowing and urge to swallow with 8 s stimulation at the optimal frequency and mode of stimulation will be measured.

iv. Stimulation Duration: We will determine the stimulation durations applied by patients when they are instructed to initiate swallowing during stimulation using the parameters identified for stimulation in i, ii and iii. The time required for them to

[figure not shown]
initiate swallowing after the onset of stimulation will be measured using air filled bellows wrapped around the neck to identify swallowing timing after stimulation onset (Figure 5). Air filled bellows are required as vibratory stimulation will interfere with accelerometry; we have used these bellows previously to identify swallowing in fMRI⁴². Additionally oral pressure sensor in using a small tube placed on the anterior tongue will may be used to identify swallows. Neck calipers will measure tissue thickness in the throat area overlying the thyroid cartilage which may affect sensory input. When the participant has completed their final session, they will mark on a visual analogue scale of 0 to 100 their level of interest in using the self-training device at home for swallowing therapy.

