Assignment to Studies. Participants will be recruited into the studies planned for Aim 1 in the order that we conduct the studies. The first study, study i, will compare the effects of motors at frequencies of 30, 70, 110, 150, 70/110 Hz, and other similar hybrid motors and measure the degree of *urge to swallow*, comfort level and frequency of swallowing during intervals following stimulation. To identify swallowing, noninvasive recordings will involve of bi-axial accelerometry of laryngeal motion, inductive plethysmography of respiration, and video recordings will identify laryngeal movement and respiratory apnea to confirm swallows. Total testing time for this first study will not exceed 1 hour; if a participant becomes fatigued we will stop the testing. Fifteen participants will be recruited and tested to evaluate different motor frequencies in study i. The testing for study ii comparing continuous versus pulsed stimulation will be conducted along with study iv determining how long stimulation is needed for a participant to initiate swallowing after stimulation, as these two studies combined will require about 1 hour. These studies will also involve 15 participants, some of who may have participated in study i. Finally, study iii will also require no more than 1 hour and will compare the effects of different neck band pressures in 15 participants some of whom may have participated in studies i, ii or iv.

We will try to accommodate participants' needs and prevent fatigue or inconvenience by dividing up the testing conditions or conducting the testing in their home if they prefer. All of our equipment is portable, including suctioning, which will allow us to travel to the participants' environments either at home, or in a nursing or rehabilitation setting. Only nasoendoscopy is restricted to the hospital environment and will only be conducted if ordered by a physician.

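### The protocol contradicts itself on where study iv falls: run before study iii, as Assignment to Studies has it, its instruction to swallow on stimulation can carry over into the swallowing rates used to choose pressure

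*Protocol*

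**What the plan says.** **Protocol, Research Design Aim 1.** Studies ii and iii measure swallowing rate and rated urge to swallow under stimulation, to choose the mode (ii) and the neck pressure (iii). Study iv has a different task. It records "the stimulation durations applied by patients when they are instructed to initiate swallowing during stimulation", and takes its stimulation settings from i, ii and iii. Counter-balanced order is stated for the frequencies in i and the two modes in ii. None is stated for the three pressures in iii.

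**Protocol, Human Subjects Protection for Aim 1, Assignment to Studies.** "Participants will be recruited into the studies planned for Aim 1 in the order that we conduct the studies". Study i is named as the first. Then: "The testing for study ii comparing continuous versus pulsed stimulation will be conducted along with study iv", "as these two studies combined will require about 1 hour". Then: "Finally, study iii will also require no more than 1 hour", with "15 participants some of whom may have participated in studies i, ii or iv".

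**Protocol, Potential Risks.** A participant may do more than one study in a single visit.

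**Protocol, Expected Outcomes and Power Analyses.** Conditions are compared within patients, with 15 patients per experiment.

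**The concern.** Studies ii and iii count swallows as a response to stimulation. The recordings (accelerometry, respiratory plethysmography, video) show that a swallow occurred. They are not described as telling a deliberate swallow from an evoked one. A participant who has been told in iv to swallow when the device is on may go on doing so in a later rate measurement, and those swallows would be counted.

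The two sections differ on whether this can happen. If iv is run last, as its own description implies, it cannot. If Assignment to Studies is followed, it can for anyone who does iv and then iii. At stake is the choice of pressure, and conditionally of mode, that goes forward to the Phase II device.

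**Working it through.** **1. The plan's own figure.** Inputs from Expected Outcomes and Power Analyses: change 2.0 − 1.2 = 0.8 swallows/min, SD of differences 0.9, alpha 0.025, power 0.80. Effect size 0.8/0.9 = 0.889 (the plan uses 0.88). A paired t-test, two-sided at 0.025, needs n = 15, with power 0.804 at 0.88. The stated 15 reproduces, and the present point does not depend on it.

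**2. The two orders side by side.**

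| | Research Design Aim 1, iv | Assignment to Studies |
|---|---|---|
| iv relative to ii | after (uses the mode found in ii) | same block, order not stated |
| iv relative to iii | after (uses the pressure found in iii) | before; iii is last |
| Can iv participants enter iii? | does not arise | yes, number not limited |

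The second and third rows cannot both be followed. Under Assignment to Studies, iv would also run before the pressure it is meant to use had been identified.

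**3. Is overlap likely?** If ii and iv share their 15 people, there are 15 (i) + 15 (ii and iv) + 15 (iii) = 45 places. With the planned 30 to 40 participants, 45 − 40 = 5 to 45 − 30 = 15 places go to repeat participants. Some repeats may come only from study i, and at the form's maximum of 45 no reuse would be needed. Reuse is therefore planned, but the share entering iii from iv is not fixed.

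**4. What carry-over does to a within-patient comparison.** For participant *i* in condition *k*, tested at position *t*, write

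rate = (own level)ᵢ + (condition effect)ₖ + cᵢ(t, k),

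where c is the extra rate from deliberate swallows. The difference between conditions *a* and *b* is

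(effect a − effect b) + [cᵢ(t_a, a) − cᵢ(t_b, b)].

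- *Uniform c:* the bracket is zero. The rates rise but the comparison is unaffected.
- *c wanes over the session:* the bracket depends on order. Counter-balancing in ii largely averages this out across the two modes. If the pressures in iii were given in a fixed order, the decline would be confounded with pressure. With a share p of the participants exposed, the mean bias would be p × [c(earlier position) − c(later position)].
- *Ceiling:* study i states 28 bursts of 8 s with 15 s rest, 28 × 23 s = 644 s = 10.73 min. One swallow on every burst is 28/10.73 = 2.61 per min. A participant swallowing at about every burst has little room to show a difference between conditions, so true differences are compressed. Study iii states 8 s stimulation but no burst count or condition length, so this schedule is only assumed to apply there.

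**5. Which study is exposed.** For iii, the route follows directly from Assignment to Studies for anyone who did iv first. For ii, it exists only if iv is run before ii within the shared block. The text does not say that, and the description of iv points the other way.

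**The case against.** The strongest reply is that the description of iv already places it after ii and iii, because it needs their results. Read that way, nothing carries over. That is fair, and it limits the point: the firm finding is a conflict of order, and carry-over follows from only one side of it. But Assignment to Studies is the section that says who is tested when, and it is explicit that iii comes after iv.

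Other replies also stand in part:

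- Comparisons are within patients, so a general rise in swallowing cancels. Bias needs waning, a ceiling, or a carry-over that differs by condition.
- Overlap into iii is optional, and participation may spread over a month or two, so the instruction may have faded. Against that, several studies may be done in one visit.
- Study iv instructs; it does not train. The protocol says repeatedly that the device is not used for training here.

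A reader might infer a size. Since 0.8 × 10.73 = 8.6 swallows and 8.6/28 = 31%, deliberate swallows on 31% of bursts would match the assumed effect. The documents do not support using this as a measure of harm. The 0.8/min is stimulation against no stimulation, whereas ii and iii compare active conditions with each other. It is a level shift, which cancels if uniform. No carry-over proportion is given anywhere.

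A reader might also want a script telling participants not to swallow because the device has come on. That would ask them to suppress the response being measured.

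**Conclusion.** The two sections conflict on where study iv falls, and the conflict should be resolved. If Assignment to Studies is followed, people already told to swallow on stimulation can contribute to the rates that choose pressure in iii. The same holds for mode in ii only if iv is run first in the shared block.

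The size of any carry-over is unknown. Harm to the comparison rests on three assumptions: that some participants do iv before iii, that the instructed response persists into the later measurement, and that it wanes, meets a ceiling or differs by condition. The documents do not support the stronger reading that both the mode and the pressure choices are contaminated by design. The weakest place is iii, where the order conflict coincides with no stated counter-balancing. Because the results select device characteristics for Phase II and the remedy is nearly free, the change is worth making.

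**What to change.** In Assignment to Studies, reconcile the order with the description of study iv:

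1. State that in any participant all swallowing-rate measurements (ii, and iii if they take part) are completed before any iv instruction is given. Running iv last as a study does this and also lets iv use the pressure found in iii.
2. Or else state that iii enrols only people who have not done iv. This closes the route into iii, but ii must still precede iv within the shared block, and the reference in iv to parameters from iii must then be reconciled separately.
3. Counter-balance the order of the three pressures in iii, as is done in i and ii. With 15 participants, three rotated orders of 15/3 = 5 people each put every pressure in every position equally often.
4. Record prior iv exposure for every participant in ii and iii, including any already tested.

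Cost: under item 1, iv testing moves out of the combined hour with ii, usually to a later visit. Under item 2, iv participants cannot be reused in iii, which may require a few more recruits. Sample size per study, equipment and outcome measures do not change.

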All participants are expected to be at increased risk of aspiration in their daily living because of their swallowing disorder independent of the study. The speech pathologists conducting the testing for the research will provide all participants and their caregivers with usual guidance on a daily regimen to follow for preventing aspiration of their own secretions. Each participant will be taught a daily regimen of oral hygiene to minimize oral bacteria. Participants and their caregivers will be taught how to test voice quality during the day in order to detect a wet, gurgly voice quality which would indicate increased fluid in or around the airway. They will be shown how to clear the airway by throat clearing, coughing and spitting into a cup and to clear the airway whenever they suspect increased fluid in or around the airway. All participants and their caregivers will be trained to monitor body temperature daily and contact the research staff if they have a rise in body temperature over three days sequentially while participating in the research. The medical officer for the project, who is not directly involved in the research, will evaluate pneumonia and other medical problems as they arise in participants in the research. It is expected that a participant will be enrolled in the study for about 1 month before being discharged from the study.

If a participant has incidental findings while participating in the research, they will be referred to the medical officer, [name], PhD, FACP, FHM, Medical Director, Hospital Division at

Rockingham Memorial Hospital. [name] will serve as the medical officer and will evaluate any medical problems as they arise in participants. He will follow internal RMH hospital policies for incidental findings, e.g. providing referrals to specialists, and following state requirements for other incidental findings such as domestic abuse.

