Participants or their caregivers will be contacted within 2 days following a test session to record their status and any difficulties following testing. The findings will be recorded in CRFs in LabTrack. All participants in the project will be asked to take their body temperature daily and to contact the PI or speech pathologist if their temperature is elevated for 3 days in sequence while participating in the project. If a participant has had an elevated temperature for 3 days in sequence they will be scheduled

to see the medical officer for the study, a [name], who is Medical Director of the Hospital Division at Rockingham Memorial Hospital, who will evaluate the patient.

Records of adverse events (AE) will be evaluated by the medical officer, [name], the Study Team and the JMU and RMH IRBs for participants in the protocol and submitted to the safety officer at NIDCD on a quarterly basis. Serious adverse events (SAE) will be evaluated by [name] and reported to the IRBs at JMU and RMH and the NIDCD Safety Officer within 10 days of their occurrence.

The IRBs will evaluate the reports of AEs/SAEs to determine if use of the device shows increased risk of aspiration pneumonia and other problems indicating that use of the device produces "more than minimal" risk.

ClinicalTrials.gov requirements

This is a Phase I safety intervention trial assessing participants' preferences on various device characteristics. None of the participants will be using any of the devices for self-training or dysphagia therapy in this trial. As this study is not a treatment trial, participants may continue their usual regimen of dysphagia therapy while participating in the study.

All participants will be monitored for AE/SAEs while participating in the study; it is expected that participants will undergo 3 or more visits of 1 hour each to provide feedback on the devices to the investigators over a 1-2 month period. On completion of the experiments a participant will be discharged from the study.

Human Subjects Protection for Aim 2: Identifying Delivery Points for Introducing Patients to Swallowing Self-training to be conducted by Passy Muir, Inc.

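### The three-day temperature rule and adverse event monitoring stop at discharge, and no stretch of participation after the last session is fixed that is long enough for the rule to work

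*Protocol*

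**What the plan says.** Four statements in the Protocol bear on this.

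- **Temperature rule.** Under Data Safety Monitoring, participants take their temperature daily and are asked "to contact the PI or speech pathologist if their temperature is elevated for 3 days in sequence while participating in the project". A participant who meets the rule is scheduled to see the medical officer. Protections against risk gives the same limit: participants and caregivers are to "contact the research staff if they have a rise in body temperature over three days sequentially while participating in the research".
- **Adverse events.** ClinicalTrials.gov requirements states: "All participants will be monitored for AE/SAEs while participating in the study".
- **End of participation.** The same section ends: "On completion of the experiments a participant will be discharged from the study". No day is given. Protections against risk adds: "It is expected that a participant will be enrolled in the study for about 1 month before being discharged from the study".
- **Follow-up after a session.** Under Data Safety Monitoring, participants or caregivers are "contacted within 2 days following a test session to record their status and any difficulties following testing". No other follow-up is timed from a session.

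The records have a stated use: "The IRBs will evaluate the reports of AEs/SAEs to determine if use of the device shows increased risk of aspiration pneumonia". Protections against risk also makes it one purpose of the trial to learn how much risk device use brings.

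**The concern.** A rule that needs three consecutive daily readings can work after an exposure only if it stays in force long enough to collect them. Here it lapses when participation ends, and participation is tied to finishing the experiments, with no interval after the last session. Earlier sessions are generally covered while further visits are pending. The final session has no such assurance, and because a person may join just one of the four studies (Potential Risks), the final session may also be the only one.

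At stake is the completeness of the safety record on which the IRBs are to judge aspiration pneumonia risk. The comparisons of swallowing rate, urge to swallow and comfort do not depend on it.

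**Working it through.** The Protocol gives no figure of its own to reproduce. The check is a count of days.

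**Inputs**

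- Trigger: 3 elevated days in sequence (Data Safety Monitoring; Protections against risk).
- Period in force: while participating (same places). AE/SAE monitoring has the same limit (ClinicalTrials.gov requirements).
- End of participation: completion of the experiments, no day stated (ClinicalTrials.gov requirements).
- Only follow-up timed from a session: within 2 days (Data Safety Monitoring).
- Expected enrolment: about 1 month (Protections against risk). Expected visits: 3 or more over 1 to 2 months (ClinicalTrials.gov requirements).
- Aim 1 participants: 30 to 40 (Expected Outcomes and Power Analyses; Recruitment and Informed Consent).

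**Step 1: when the rule is met.** Let the last session be day 0 and let participation end on day D. A fever first read on day k has elevated readings on days k, k+1 and k+2, so the rule is met on day k+2. It can be met during participation only if k + 2 ≤ D, that is, k ≤ D − 2.

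**Step 2: results by day of discharge.**

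| Participation ends on day D | Latest first reading that can meet the rule (D − 2) | Days of first reading covered, from the session on |
|---|---|---|
| 0 | −2 | none |
| 2 | 0 | day 0 only |
| 3 | 1 | days 0 to 1 |
| 5 | 3 | days 0 to 3 |
| 7 | 5 | days 0 to 5 |

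**Step 3: what is guaranteed.** Discharge on completion, taken literally, gives D = 0. If the follow-up contact counts as participation, its deadline guarantees no more than D = 2. In both cases D − 2 ≤ 0, so a fever first read on day 1 or later is not sure to be able to meet the rule. A first reading on day 1 needs D ≥ 3.

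**Step 4: what the expected month adds.** Suppose enrolment lasts M days and the last session falls on enrolment day L. Then D = M − L, and a fever first read on day 1 is covered only if M − L ≥ 3, that is, L ≤ M − 3. Taking M = 30 (an assumption; the Protocol says only about one month), L ≤ 27. Each day by which the true figure differs from 30 moves this limit by one day. The visits themselves are expected to run over 1 to 2 months, so a last session on day 30 or later is also plausible, and then the month leaves 30 − 30 = 0 days or fewer. The month therefore covers some schedules and not others.

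**The case against.** The best case for the plan has four parts.

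1. *The 2-day contact does not end participation.* This is right. A reader might infer that participants leave within 2 days of the last session. The text does not say so: it sets a deadline for a call and does not link the call to discharge. It shows only that no more than 2 days are guaranteed. Discharge may in practice come later, and the expected month may cover many people, including some who attend once.

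2. *The three-day rule is not the only way a fever is noticed.* This also stands. A reader might infer that a fever after the last session would go unseen. But the contact asks about status and difficulties, so a fever already present on the day of the call can be reported without three readings. Participants and caregivers are also taught voice checks and airway clearing, and the medical officer "will evaluate pneumonia and other medical problems as they arise in participants in the research". Observation is reduced, not absent. What remains is that the call may be made as early as day 0 or 1 and cannot record a fever that begins after it.

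3. *The risk is small.* Only saliva is swallowed, suction is available and phonation is checked every 10 to 12 minutes. This bears on how serious the point is. It does not explain why a safeguard the Protocol chose for itself should lapse after the final exposure.

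4. *This is detail that may be set elsewhere.* The consent pages are not in the text reviewed and might say how long to log temperature. Even so, the Protocol itself fixes the limit on the rule and the discharge event. The weakness comes from how those two statements combine, and safety follow-up and discharge are protocol matters.

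**Conclusion.** The point holds as a minor weakness. Followed as written, the discharge rule can end the temperature rule and AE/SAE monitoring before a fever first read on day 1 or later could meet the three-day trigger. Participation to day 3 is the least that would be needed, and no more than 2 days are guaranteed.

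The size is one final session for each of 30 to 40 participants, with an unknown share actually lacking cover. It would be wrong to conclude that all participants lack cover, or that pneumonia events will be missed in any stated number: the Protocol gives no rate or timing of pneumonia after a session from which to estimate this.

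The conclusion rests on one daily reading, on counting the third elevated day as the day the rule is met, and on the discharge and enrolment sentences meaning what they say. The 30-day month is an assumption used only to show that cover from the expected enrolment is possible and not assured.

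**What to change.** In Data Safety Monitoring and ClinicalTrials.gov requirements, state that daily temperature logging, the three-day reporting rule and AE/SAE monitoring continue for a fixed period of more than 3 days after each participant's last session. At least 5 days would cover a fever first read by day 3 (5 − 2 = 3). This is an example, and the medical officer should set the length. Add a closing telephone contact at the end of that period, with discharge only afterwards, and align the enrolment and temperature sentences in Protections against risk.

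The cost is a wording change, a few more days of a task participants already perform, and one re-timed or repeated call per participant. The downside is slightly longer enrolment.
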